7.8.2 Subgroup analysis by Study Region (Japan, Korea, Taiwan)

Following efficacy, safety, and pharmacodynamic variables will be analyzed by Study Region (Japan, Korea, Taiwan) in addition to 7.8.1 Subgroup analysis.

- o ACR50
- o ACR70
- DAS28-CRP
- o DAS28-ESR
- o HAQ-DI
- o SF-36V2®
- Overview of TEAEs
- Serious TEAEs
- Drug related TEAE
- TEAE leading to permanent discontinuation of study drug
- The number and percentage of subjects with TEAEs of special interest
 - Serious Infections
 - Malignancies
 - Herpes Zoster Related Disease (Herpes Zoster and Varicella)
 - Herpes Zoster
 - Varicella
 - Infections That Require Intravenous Anti-infectious Therapy
- Clinical Laboratory Evaluation

- For continuous variables, descriptive statistics of raw values, change from Week 0 value at each scheduled visit will be summarized at each time point using SI unit
- For categorical variables, frequencies and percentages will be displayed at each scheduled visit.
- o Pharmacodynamic variables
 - Described in 7.7

7.9 Other Analyses

Not Applicable.

7.10 Interim Analysis (and Early Discontinuation of the Clinical Study)

Not applicable for efficacy analysis. Review of safety data and safety evaluation will be conducted by an independent DSMB during the study in accordance with separate SOP.

7.11 Handling of LLOQ, Missing Data, Outliers, Visit Windows, and Other Information

7.11.1 LLOQ

Safety variables

Values below the LLOQ for beta-D-glucan, hCG, Troponin-T, CK-MB will be treated as it is and these variables are not used for descriptive statistics and displayed in the listings. As for beta-D-glucan, it is used for shift-from baseline analysis.

PD variables

Values below the LLOQ will be set to 0 for calculation of descriptive statistics.

7.11.2 Missing Data

Missing Data in ACR20/50/70, DAS28

Table below addresses the handling of missing ACR components and ACR response in analyses of ACR20/50/70, DAS28, and DAS28-related variables at ET. Note that if subject does not have any post-baseline values, then that subject will be defined as a non-responder.

Imp	outation Method	Explanation/Instruction	
For u	For use in all ACR20/50/70 analyses at ET		
1	LOCF components	LOCF all ACR component value(s) at the last evaluation point and then calculate ACR response as ET.	
For u	For use in all DAS28 and DAS28-based analyses at ET		
2	LOCF components	LOCF all DAS28 CRP component value(s) at the last evaluation point and then calculate the DAS28 score as ET.	

Missing Data in HAQ-DI

For HAQ-DI, there are 20 items in 8 categories, with each category having 2 or 3 questions. A subject must have a score in >= 6 of the 8 categories, otherwise the HAQ-DI cannot be computed and will be considered missing for data summarization and analysis purposes. If responses to individual questions within a category are missing, they are not imputed. Therefore, the score in each category is based on non-missing responses. A category score is missing when all responses within a category are missing.

Missing Data in SF-36v2

For SF-36v2, there are 8 scales (domains). Missing values will be imputed if at least half of the items in the domain that included the missing item score(s) are non-missing. In that case, the missing value will be imputed with the average score of the non-missing item scores in this domain.

Missing Data in FACIT-Fatigue

For FACIT-Fatigue, there are 13 items. Missing values of any individual item will be imputed with the average score obtained from the non-missing items if more than 50% of the items are available, i.e., if the number of non-missing items >= 7.

Missing Data in WPAI

For WPAI Scale Score, each score will be computed on condition that the all of the questions for each score will not be non-missing.

Safety Data Imputation Methods

For safety data, LOCF method will be used for the value at ET.

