- o. SF-36v2® is administered every 4 weeks until Week 48 and every 24 weeks after Week 48 to subjects from study RAJ1 and every 24 weeks throughout the study period to subjects from studies RAJ3 or RAJ4.
- p. WPAI is administered only to subjects who transferred from studies RAJ3 or RAJ4.
- q. AEs must be collected from the time of the administration of the first dose of study drug to the end of all assessments at the end of study (at time of follow-up).
- r. After all of the assessments and tests scheduled for Week 0 have been completed, the subjects will receive the first dose of the study drug at each study center.
- s. [Subjects who transferred from study RAJ1] If the study is terminated before the Week 48 visit, the specified date for the study visit at the end of treatment will be the date of the previous visit + 28 days (allowable range, ± 7 days). If the study is terminated in or after the Week 48 visit, the specified date for the

12-Nov-2019 Astellas Page 12 of 94

study visit at the end of treatment will be the date of the previous visit + 84 days (allowable range, \pm 14 days).

[Subjects who transferred from studies RAJ3 or RAJ4] The specified date for the study visit at the end of treatment will be the date of previous study visit \pm 84 days (allowable range, \pm 14 days).

- t. For unscheduled visits, these assessments and tests should be performed only if clinically indicated as determined by the investigator.
- u. In principle, the subject should visit the study center on the specified date. If it is not possible for subjects to visit the study center on the specified date, the date of the visit should be adjusted to the date closest to the reference date as possible.
- v. Only subjects who transferred from study RAJ1 should make study visits at Weeks 2, 4, 8, 16, 20, 28, 32, 40, and 44.
- w. At visits after Week 132, the tests and assessments shall be performed in the same manner as scheduled for Weeks 96 to 132.
- x. Chest radiography at the end of treatment/early termination is not necessary if one has been taken within 24 weeks from the day of the end of treatment/early termination.

12-Nov-2019 Astellas Page 13 of 94

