7 STATISTICAL METHODOLOGY

7.1 General Considerations

- For continuous variables, descriptive statistics will include the number of subjects (n), mean, standard deviation (SD), median, minimum, and maximum.
- For categorical variables: number and percentages of subjects will be described.
- For time-to-event variables: number and percentage of subjects with the event using Kaplan-Meier method, the cumulative event rate will be estimated and a plot will be constructed.
- All data processing, summarization, and analyses will be performed using SAS Drug Development (ver. 4.5), and PC-SAS (ver. 9.4) or higher versions.
- Specifications for table, figures, and data listing formats can be found in the TLF specifications for this study.
- For the definition of subgroups of interest can be referred to Section 7.8.
- Summaries based on FAS and SAF (e.g. disposition, baseline, efficacy data and safety data) will be presented by preceding studies and overall, unless specifically stated otherwise.
- Medical Dictionary for Regulatory Activities (MedDRA) 11.1 will be used as the coding dictionary for adverse event and medical history.
- Confidence interval for binary outcome is continuity corrected in all analysis.
- For the analyses of efficacy and pharmacodynamics variables in this extension study, values at the baseline in the preceding studies (RAJ1, RAJ3, and RAJ4) will be used as the baseline values. However, changes from baseline values of this extension study will also be examined where appropriate. For the analyses of safety, Week 0 of this extension study will be referred to as the baseline; however, changes from baseline values of the preceding studies (RAJ1, RAJ3, and RAJ4) will also be examined where appropriate.
- Change from baseline to post-baseline will be calculated as: post-baseline value baseline value. If the baseline value is missing, then that subject is not included in the calculation at any visit.
- Percent change from baseline to post-baseline will be calculated as: 100 × (change /baseline). If the baseline value is 0 or missing, or post-baseline value is missing, then percent change from baseline to post-baseline is missing.
- The values below the lower limit of quantitation (BQL) for β-D-glucan, hCG, Troponin, CK-MB will be treated as it is and these variables are not used for descriptive statistics

- and displayed in the listings. As for β -D-glucan, it is used for shift-from baseline analysis.

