10.7 Appendix 7: Computation of WPAI Scale Score

Work Productivity and Activity Impairment Questionnaire: WPAI

In this study, the following scoring methods are applied. These scoring methods are based on the specific health problem version of WPAI (WPAI:SHP).

Question	
Number	Contents
1.	1. Are you currently employed (working for pay)?
2.	2. During the past seven days, how many hours did you miss from work because of problems associated with your rheumatoid arthritis?
3.	3. During the past seven days, how many hours did you miss from work because of any other reason, such as vacation, holidays, time off to participate in this study?
4.	4. During the past seven days, how many hours did you actually work?
5.	5. During the past seven days, how much did your rheumatoid arthritis affect your productivity while you were working?
6.	6. During the past seven days, how much did your rheumatoid arthritis affect your ability to do your regular daily activities, other than work at a job?

Scores:

Multiply scores by 100 to express in percentages.

- Percent work time missed due to problem: Q2/(Q2+Q4)
- Percent impairment while working due to problem: Q5/10
- Percent overall work impairment due to problem: Q2/(Q2+Q4)+[(1-(Q2/(Q2+Q4))x(Q5/10)]
- Percent activity impairment due to problem: Q6/10

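### The WPAI completeness rule in SAP 7.11.2 is inverted as printed; read as intended, it sets overall work impairment to missing for a worker fully absent because of RA who leaves Question 5 blank, although the SAP formula fixes that score at 100%

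*SAP*

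**What the plan says.** WPAI applies to part of the population: "WPAI is administered only to subjects who transferred from studies RAJ3 or RAJ4" (SAP section 2, schedule footnotes). Protocol 2.3.2 lists change from baseline in WPAI as an efficacy variable for these subjects. SAP Appendix 1 (row 15) plans raw values and change from the preceding study's baseline at each visit, without hypothesis tests.

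The only WPAI rule for missing answers is in SAP 7.11.2: "each score will be computed on condition that the all of the questions for each score will not be non-missing".

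SAP Appendix 7 defines four scores. The inputs that matter here are:

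- Question 2: "2. During the past seven days, how many hours did you miss from work because of problems associated with your rheumatoid arthritis"
- Question 4: "4. During the past seven days, how many hours did you actually work"
- Question 5: "how much did your rheumatoid arthritis affect your productivity while you were working"

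The first score is "Percent work time missed due to problem: Q2/(Q2+Q4", followed by its closing parenthesis. The combined score is printed as "Percent overall work impairment due to problem: Q2/(Q2+Q4)+[(1-(Q2/(Q2+Q4))x(Q5/10", followed by one closing parenthesis and one square bracket. That makes five opening and four closing round parentheses. The other two scores are impairment while working (Q5/10) and activity impairment (Q6/10).

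For change scores, SAP 7.1 adds: "If the baseline value is missing, then that subject is not included in the calculation at any visit". The efficacy baseline is that of the parent study.

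Neither document prints a skip instruction for Question 5, a rule for Q4 = 0, or a rule for Q2 + Q4 = 0.

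**The concern.** Taken literally, the completeness rule refuses to score a complete questionnaire. The HAQ-DI, SF-36v2 and FACIT-Fatigue rules in the same section can be programmed as they stand; this one has to be reinterpreted first.

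The more substantive matter remains after that reinterpretation. Requiring every question makes overall work impairment depend on Question 5 even where Question 5 has no effect on the result. A subject who worked no hours because of RA has no productivity at work to rate and may leave the item blank. Missingness would then be caused by the worst possible outcome, so any error runs one way, towards less impairment. If it happens at the parent-study baseline, the SAP 7.1 rule removes that subject from the change analysis of this score at all visits, including any return to work.

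**Working it through.** The plan states no figure to reproduce here: no sample size, power or test concerns WPAI. The check applies the SAP's own formula and rules to example records, written as (Q2, Q4, Q5).

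**1. The completeness rule.** The printed words can mean that not all questions are answered, or that all are unanswered.

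| Record | Intended rule (all answered) | Literal: not all answered | Literal: all unanswered |
|---|---|---|---|
| (8, 32, 4) | scored | not scored | not scored |
| (40, 0, blank) | not scored | scored | not scored |
| all blank | not scored | scored | scored |

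Both literal readings reject complete records and admit empty ones. Neither is workable, so the intended meaning is clear.

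**2. The parenthesis.** Let a = Q2/(Q2+Q4). The missing parenthesis can close in two places:

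- after the inner fraction: a + (1 − a) × Q5/10
- at the end: a + (1 − a × Q5/10)

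| Record | Closed after the fraction | Closed at the end |
|---|---|---|
| (0, 40, 2) | 0 + 1 × 0.2 = 20% | 0 + 1 = 100% |
| (8, 32, 5) | 0.2 + 0.8 × 0.5 = 60% | 0.2 + 0.9 = 110% |
| (40, 0, 0) | 1 + 0 = 100% | 1 + 1 = 200% |
| (40, 0, 10) | 1 + 0 = 100% | 1 + 0 = 100% |

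The second closure exceeds 100% on a percentage scale, so only the first can be meant.

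**3. The fully absent worker under the intended rule.** With Q2 > 0 and Q4 = 0, a = 1. Overall impairment is then 1 + (1 − 1) × Q5/10 = 100%, whether Q5 is 0, 5 or 10. With Q5 blank, the all-answered rule sets this determined value to missing. By comparison, (39, 1, 0) is kept at 0.975 + 0.025 × 0 = 97.5%.

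For the same subject the other scores behave as follows:

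- Work time missed needs only Q2 and Q4, so it is kept at 100%.
- Activity impairment needs only Q6, so it is kept.
- Impairment while working has no meaningful value, so missing is right.

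**4. Possible size.** The documents give neither the share of employed subjects who are fully absent (s), nor the fraction of those with Q5 blank (b), nor the mean score of the others (m). All three are assumed.

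- Mean with everyone kept: 100s + m(1 − s)
- Reported mean: [100s(1 − b) + m(1 − s)] / [s(1 − b) + (1 − s)]
- With b = 1, the difference reduces to s(100 − m).

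Understatement in percentage points with m = 30:

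| s | b = 0 | b = 0.5 | b = 1 |
|---|---|---|---|
| 1% | 0 | 0.3 | 0.7 |
| 3% | 0 | 1.0 | 2.1 |
| 5% | 0 | 1.7 | 3.5 |
| 10% | 0 | 3.3 | 7.0 |

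For example, with s = 10% and b = 1 the full mean is 10 + 27 = 37.0 and the reported mean is 30.0. At that corner, m = 20 gives 8.0 points and m = 40 gives 6.0.

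**5. Undefined case.** When Q2 + Q4 = 0, for example after a week away entirely for other reasons (Question 3), the fraction is 0/0. The SAP does not say what happens.

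**The case against.** The strongest reply is that two of the three defects are editorial. A rule that scores blank forms cannot be programmed sensibly, and a formula that yields 110% or 200% would be noticed. That stands. A reader might infer that complete questionnaires would go unscored or that impairment would be reported above 100%, but each slip has only one workable reading, so the documents do not support either expectation.

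The reply to the remaining gap is that a blank Question 5 is inferred. Appendix 7 lists the six questions without a skip instruction, and no case report form page is shown. If any Question 5 value was recorded, the subject scores 100% and nothing is lost. This also stands; it is why the lower end of the range is zero.

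A reader might also infer that fully absent workers vanish from the WPAI results, or that a move into or out of full absence is never seen. The documents do not support that. Work time missed keeps these subjects at 100% and shows such a move, activity impairment is unaffected, and the SAP 7.1 exclusion acts only on the score whose baseline is missing.

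Finally, WPAI is one descriptive row for RAJ3 and RAJ4 transfers, and no study conclusion depends on it. Subjects entering RAJ2 had completed 52 weeks and wished to continue, so whole-week absence because of RA may be uncommon during the extension. That is less reassuring for the parent-study baseline. These points limit the importance of the gap but do not close it: the intended rule still discards a score that the recorded answers fully determine.

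**Conclusion.** The concern holds in a limited form. The completeness sentence and the parenthesis are wrong as printed and need editorial correction. Under the intended rule, percent overall work impairment is set to missing for an employed subject with Q2 > 0, Q4 = 0 and Question 5 blank, although the SAP's formula gives 100%. The loss affects that score only and can only lower its mean. If it occurs at the parent baseline, the subject leaves that score's change analysis entirely.

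The size is unknown. The 0 to 7 point range rests on an assumed 1% to 10% of employed subjects fully absent, an assumed mean of 30% in the others, and anything from none to all of the Question 5 answers blank. The documents support no narrower figure and no claim about the study's conclusions.

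**What to change.** In SAP 7.11.2, replace the WPAI sentence with:

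*Each WPAI score is computed only if all questions needed for that score are non-missing. If Q1 = yes, Q2 > 0 and Q4 = 0, percent overall work impairment = 100% whether or not Q5 is answered. If Q2 + Q4 = 0, percent work time missed and percent overall work impairment are missing.*

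In Appendix 7, print the combined score as Q2/(Q2+Q4) + [(1 − Q2/(Q2+Q4)) × (Q5/10)].

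Apply the same rule to the RAJ3 and RAJ4 baseline WPAI records. How those studies scored WPAI is not in these documents, and changing RAJ2 alone could put baseline and follow-up on different rules.

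The cost is a few lines of SAP text and one parenthesis, plus rescoring the parent baselines from their item answers. No new data are collected.

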- In addition, for the selected laboratory tests (hematology, biochemistry, fasting lipid profile), descriptive statistics of raw values and change from baseline of preceding study at each visit will be summarized similarly. In this analysis, time course of each safety variable will be presented from baseline of preceding study up to end of RAJ2 study by Treatment Sequence Set. Following analysis visits of preceding study will be used,
- Subjects shifted from RAJ1
 - o RAJ1 Week 0
 - o RAJ1 Week 12
 - Week 0 (RAJ1 Week 16)

- Subjects shifted from RAJ3/4
 - \circ RAJ3/4 Week 0
 - o RAJ3/4 Week 12
 - o RAJ3/4 Week 28
 - o RAJ3/4 Week 40
 - o RAJ3/4 Week 52
 - o Week 0
- Shift-from-Week 0 table: Shift from Week 0 to highest value, and Shift from Week 0 to lowest value during entire period, for all laboratory variables. If the laboratory value of same subject is measured lower from normal range at one visit, and higher from normal range at the other visit, that subject will be counted as both low and high from Week 0 during entire period.
- Graphical analysis:
 - The mean-standard deviation plot of actual values and changes from week 0 will be presented for the selected laboratory tests (hematology, biochemistry, fasting lipid profile).

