7.5.3 Vital Signs

Raw values and changes from Week 0 at each scheduled visit will be summarized using descriptive statistics.

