7.5.4 Electrocardiograms (ECGs)

<12-lead ECG>

• Raw values (categorical) and changes from Week 0 (shift from Week 0) will be summarized, and the summaries will include number and percentage of subjects with normal, not clinically significant abnormal and clinically significant abnormal 12 lead ECG findings.

^(*) Combination of values measured within same sample

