7.11.4 Visit Windows

The acceptable time ranges of the efficacy and safety examinations, observations, etc. from the date of initial study treatment (Day 1) are defined as follows. If there are multiple data available over the same period of time, the data obtained on the day closest to the reference date will be utilized; the later date will be applied if the number of days from the reference date is equal. Missing data at the end or discontinuation of treatment will be imputed using the LOCF method.

Since the study period of this study differs depending on the subject, the timing for the required visits to the study center will also differ from subject to subject. Only subjects who transferred from study RAJ1, but not those who transferred from studies RAJ3 or RAJ4, are required to come for visits at Week 2, Week 4, Week 8, Week 16, Week 20, Week 28, Week 32, Week 40, and Week 44. Therefore, these time points defined in the analysis are set only for the subjects from study RAJ1.

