7.11.6 Handling of Schedule of Assessments of Safety Variables

For data obtained after the end of study treatment, the data obtained within +2 days after the last dose will be included in analysis, except for the data at the end of the study (at time of follow-up).

(1) Vital Signs

Time points defined in analysis	Reference date*	Acceptable time range
Week 0	Day 1	Day 1
Week 2	Day 15	Day 12 to Day 18
Week 4	Day 29	Day 22 to Day 36
Week 8	Day 57	Day 50 to Day 64
Week 12	Day 85	Day 78 to Day 92
Week 16	Day 113	Day 106 to Day 120
Week 20	Day 141	Day 134 to Day 148
Week 24	Day 169	Day 162 to Day 176
Week 28	Day 197	Day 190 to Day 204
Week 32	Day 225	Day 218 to Day 232
Week 36	Day 253	Day 246 to Day 260
Week 40	Day 281	Day 274 to Day 288
Week 44	Day 309	Day 302 to Day 316
Week 48	Day 337	Day 330 to Day 344
Week 60	Day 421	Day 407 to Day 435
Week 72	Day 505	Day 491 to Day 519
Week 84	Day 589	Day 575 to Day 603
Week 96	Day 673	Day 659 to Day 687
Week 108	Day 757	Day 743 to Day 771
Week 120	Day 841	Day 827 to Day 855
Week 132	Day 925	Day 911 to Day 939
Week 132 + 12 × x	Day $7 \times (132 + 12 \times x) +$	Day $7 \times (132 + 12 \times x) - 13$ to
.,	1	Day $7 \times (132 + 12 \times x) + 15$
End/discontinuation of treatment	Day of the last dose	Day 2 to 2 days after the last dose
End of the study (at time of follow-up)	28 days after the last dose	21 to 35 days after the last dose

^{*:} Day 1 represents the first day of study treatment.

(2) Laboratory Tests (Hematology, Biochemistry [including Fasting Lipid Profile Test], Urinalysis)

Time points defined in analysis	Reference date*	Acceptable time range
Week 0	Day 1	Day 1
Week 2	Day 15	Day 12 to Day 18
Week 4	Day 29	Day 22 to Day 36
Week 8	Day 57	Day 50 to Day 64
Week 12	Day 85	Day 78 to Day 92
Week 16	Day 113	Day 106 to Day 120
Week 20	Day 141	Day 134 to Day 148
Week 24	Day 169	Day 162 to Day 176
Week 28	Day 197	Day 190 to Day 204
Week 32	Day 225	Day 218 to Day 232
Week 36	Day 253	Day 246 to Day 260
Week 40	Day 281	Day 274 to Day 288
Week 44	Day 309	Day 302 to Day 316
Week 48	Day 337	Day 330 to Day 344
Week 60	Day 421	Day 407 to Day 435
Week 72	Day 505	Day 491 to Day 519
Week 84	Day 589	Day 575 to Day 603
Week 96	Day 673	Day 659 to Day 687
Week 108	Day 757	Day 743 to Day 771
Week 120	Day 841	Day 827 to Day 855
Week 132	Day 925	Day 911 to Day 939
Week 132 + 12 × x	Day $7 \times (132 + 12 \times x) +$	Day $7 \times (132 + 12 \times x) - 13$ to
Week 132 + 12 ^ X	1	Day $7 \times (132 + 12 \times x) + 15$

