Minimum on Treatment		Minimum value during Entire
William on Treatment		Period (No limitation for period)
Maximum on Treatment		Maximum value during Entire
		Period (No limitation for period)
End/discontinuation of treatment	Day of the last dose	Day 2 to 2 days after the last dose
End of the study	28 days after the last	21 to 35 days after the last dose
(at time of follow-up)	dose	21 to 33 days after the last dose

^{*:} Day 1 represents the first day of study treatment.

(3) 12-lead ECG, Chest Radiography

Time points defined in analysis	Reference date*	Acceptable time range
Week 0**	Day 1	Day 1
Week 24****	Day 169	Day 162 to Day 176
Week 48	Day 337	Day 330 to Day 344
Week 72****	Day 505	Day 491 to Day 519
Week 96	Day 673	Day 659 to Day 687
Week 96 + 24 × x****	Day $7 \times (96 + 24 \times x) + 1$	Day $7 \times (96 + 24 \times x) - 13$ to Day $7 \times (96 + 24 \times x) + 15$
End/discontinuation of treatment***	Day of the last dose	Day 2 to 2 days after the last dose

^{*:} Day 1 represents the first day of study treatment.

^{**:} Regarding chest radiography, it is allowed to use data obtained within 28 days prior to the Week 0 visit.

^{***:} Chest radiography at the end/discontinuation of treatment is unnecessary if one has been taken within 24 weeks from the day of discontinuation.

^{****:} Only Chest radiography is applied for 24 weeks intervals (only for Taiwan).

(4) Body weight

Time points defined in analysis	Reference date*	Acceptable time range
Week 0	Day 1	Day 1
Week 2	Day 15	Day 12 to Day 18
Week 4	Day 29	Day 22 to Day 36
Week 8	Day 57	Day 50 to Day 64
Week 12	Day 85	Day 78 to Day 92
Week 24	Day 169	Day 162 to Day 176
Week 36	Day 253	Day 246 to Day 260
Week 48	Day 337	Day 330 to Day 344
Week 60	Day 421	Day 407 to Day 435
Week 72	Day 505	Day 491 to Day 519
Week 84	Day 589	Day 575 to Day 603
Week 96	Day 673	Day 659 to Day 687
Week 108	Day 757	Day 743 to Day 771
Week 120	Day 841	Day 827 to Day 855
Week 132	Day 925	Day 911 to Day 939
Week 132 + 12 × x	Day $7 \times (132 + 12 \times x) +$	Day $7 \times (132 + 12 \times x) - 13$ to
Week 132 + 12 ^ X	1	Day $7 \times (132 + 12 \times x) + 15$
End/discontinuation of treatment	Day of the last dose	Day 2 to 2 days after the last dose
End of the study	28 days after the last	21 to 25 days after the last days
(at time of follow-up)	dose	21 to 35 days after the last dose

^{*:} Day 1 represents the first day of study treatment.

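### Minor: the safety end-of-treatment row is in effect a last on-treatment value with no age limit, and vital signs and ECG lack the worst-value summaries that laboratory tests have

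*SAP*

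**What the plan says.** On the ET value, SAP 7.11.2 ends with "For safety data, LOCF method will be used for the value at ET". SAP 7.11.4 prescribes LOCF for missing end-of-treatment data in general and says that, where several values share a window, "the data obtained on the day closest to the reference date will be utilized". In the safety tables of SAP 7.11.6 the reference date of the ET row is the day of the last dose and the accepted range is "Day 2 to 2 days after the last dose". Follow-up apart, post-treatment data count only under this rule: "the data obtained within +2 days after the last dose will be included in analysis". Protocol 7.8 and 7.8.3 carry the same LOCF rule and the same ET range.

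On extreme values, laboratory tests are well covered. SAP 7.5.2.1 plans "Shift from Week 0 to highest value, and Shift from Week 0 to lowest value during entire period, for all laboratory variables", SAP 7.5.2.2 adds a shift to worst toxicity grade, and the laboratory table in 7.11.6 has a minimum row and a "Maximum on Treatment" row with no limit on period.

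For vital signs, SAP 7.5.3 says only: "Raw values and changes from Week 0 at each scheduled visit will be summarized using descriptive statistics". For ECG, SAP 7.5.4 says: "Raw values (categorical) and changes from Week 0 (shift from Week 0) will be summarized". Appendix 3 lists no highest, lowest or worst-value table for either.

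**The concern.** A reader will take the ET row as the subject's status when treatment stopped. Day 2 is counted from the first dose, so it sets a floor and does not limit how old a value may be at the last dose. LOCF adds no limit either. Observed ET results and older substitutes share one label, and the SAP plans no count of each.

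Early terminators are the most exposed, and for them the status at stopping matters most. Protocol Table 1, note d, asks for their ET assessment within 2 days of the last dose only where possible. Follow-up takes place only if the investigator thinks it necessary (notes d and e), and the ECG table in SAP 7.11.6 has no follow-up row.

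The second gap is separate. Protocol Table 1, note k, permits an unscheduled ECG after a cardiovascular adverse event. If it falls outside the scheduled windows, it appears to enter no table unless it is the value closest to the last dose. ECG is of interest for this drug: Protocol 1.4 reports QTcF shortening of 12.0 msec at 150 mg and 14.7 msec at 450 mg and calls the risk uncertain, and Protocol 3.4 makes a confirmed QTc below 300 msec a reason to discontinue.

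**Working it through.** **Inputs**
- ECG every 48 weeks and at ET: Protocol 5.4.6 and Table 1, note k.
- Vital signs at each visit: every 12 weeks for subjects from RAJ3 or RAJ4. For subjects from RAJ1, every 4 weeks from Week 4 to Week 48, then every 12 weeks (Protocol Table 1, note v).
- Window half-widths: 7 days from Week 4 to Week 48 and 14 days afterwards (SAP 7.11.6).

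**The plan's own figures first.** Reference day = 7 × week + 1.
- Week 48: 7 × 48 + 1 = 337, window 330 to 344.
- Week 96: 7 × 96 + 1 = 673, window 659 to 687.

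Both agree with the SAP tables.

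**Oldest value the ET row can show, no scheduled visit missed.** Suppose the last dose is on the day before the next assessment falls due and no usable ET assessment exists. Then age = interval between assessments − 1 day. Counting to the due date itself adds one day.
- Vital signs, 12-week schedule: 84 − 1 = 83 days (83/7 = 11.9 weeks). With both visits at opposite ±14-day edges: 84 + 14 + 14 − 1 = 111 days.
- Vital signs, RAJ1 between Weeks 4 and 48: 28 − 1 = 27 days; at the ±7-day edges 28 + 7 + 7 − 1 = 41 days.
- ECG: 336 − 1 = 335 days (335/7 = 47.9 weeks). At the edges between Weeks 48 and 96: 687 − 330 − 1 = 356 days. After Week 96: 336 + 14 + 14 − 1 = 363 days.

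**Average age.** If last doses are spread evenly between assessments (an assumption), ages run evenly from 0 to 83 or from 0 to 335 days. The means are 83/2 = 41.5 days for vital signs and 335/2 = 167.5 days for ECG.

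**When these ages apply.** The Day 2 floor excludes the Week 0 value from the window. Read that way, a subject who stops before the Week 48 ECG has no earlier scheduled ECG to substitute, and a RAJ3 or RAJ4 subject who stops before Week 12 has no earlier scheduled vital signs. The SAP does not say whether LOCF may nevertheless reach back to Week 0.

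**Late ET assessments.** The ET row closes at last dose + 2 days and the follow-up row covers days 21 to 35. A vital-sign reading taken 3 to 20 days after the last dose enters neither. An ECG taken from day 3 onwards enters no row.

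**The case against.** The best defence is that this is a deliberate convention. Protocol 7.8 prescribes LOCF at end of treatment, Protocol 7.8.3 uses the same window, and the SAP follows both. The study is open-label, without a comparator, and descriptive, and no decision hangs on the row. This stands. A reader might infer that the SAP departs from the protocol or that LOCF is an error here; the documents support neither.

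A reader might also infer that planned ET visits will drift out of the window, because Table 1, note s, counts their date from the previous visit. Note d asks for the assessments promptly after dosing ends, and Protocol 5.1.6 has subjects attend before taking that day's dose. Someone dosing up to a planned ET visit would therefore normally have taken the last dose the day before, inside the window. The problem is confined mainly to early terminators with a late or missing assessment.

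A third tempting inference is that important findings are lost. Under Protocol 5.5.1 an abnormality that is symptomatic, needs intervention or a dosing change, or is judged clinically significant is an adverse event, and adverse events are listed. That protection is real but partial. The ECG category for abnormalities short of clinical significance (Protocol 5.4.6) would normally fall outside it, although the ECG table reports that category.

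Two further cautions hold. SAP 7.1 refers table formats to separate specifications that are not available here, so counts or footnotes may exist there. SAP 7.5.4 does not name the endpoint of its ECG shift; reading it as tied to the scheduled windows rests on SAP 7.11.6 and on Protocol 7.5.4, which summarizes ECG by time point. Finally, a worst-value table does not cure an old ET value: the two gaps need separate remedies.

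**Conclusion.** The point holds as a minor, cheap improvement. The safety ET row is a last on-treatment value with no age limit, shown under a label that suggests status at stopping. In an early terminator without a usable ET assessment, the value can be up to about 12 weeks old for vital signs on the 12-week schedule, and up to about 48 weeks old for ECG once a Week 48 ECG exists. Visit-window edges add up to 28 days. These are upper limits and assume no missed scheduled visit and no intervening unscheduled reading. The documents give no count of missing or late ET assessments, so the number of subjects affected cannot be derived, and the direction of any bias is unknown.

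Separately, no worst-value summary is stated for vital signs or ECG, so an unscheduled on-treatment reading outside the visit windows may go untabulated. Whether Week 0 can be carried into the row needs only a clarifying sentence; the Day 2 floor suggests that it cannot.

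**What to change.** 1. In SAP 7.5.4 and Appendix 3, add a shift from Week 0 to the worst post-Week 0 ECG category. In SAP 7.5.3, and correspondingly in Appendix 3, add highest and lowest post-Week 0 vital signs. Include unscheduled on-treatment assessments in both. This mirrors what the SAP already does for laboratory tests.
2. In SAP 7.11.6, keep the protocol's LOCF row but label it 'last on-treatment value'. Beside it, report the observed ET result within 2 days of the last dose, with its n.
3. As clarification only, state in SAP 7.11.2 that Week 0 is not carried into the safety ET row.

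The cost is SAP wording and a few extra tables, and the observed-ET row will have a smaller n. Keeping the LOCF row preserves the analysis in Protocol 7.8. All the data are already collected.
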